(http://www.nice.org.uk/guidance/dg11) and a near-patient test has been developed (http://www.buhlmannlabs.ch/core/quantum-blue/calprotectin/). A recent meta-analysis (394 IBD/321 non-IBD controls) reported a pooled sensitivity and specificity of FC in the diagnosis of IBD in children of 0.98 (95% confidence interval: 0.95–1.0) and 0.68 (0.50– 0.86) respectively (Henderson 2014). The low specificity indicates that an alternative or additional test with higher specificity is needed to reduce the time to diagnosis and avoid many children undergoing unnecessary investigations.

There is great interest in the measurement of volatile organic compounds (VOCs) in breath and vapours from various human tissues (urine, stool, blood) in the diagnosis and monitoring of a wide range of diseases. VOCs emitted from stool are responsible for stool odour and consist of a large number of carbon based molecules of low molecular mass (<1.5Kd) including organic acids, alcohols, esters, heterocyclic compounds, aldehydes, ketones and alkanes. They result from the metabolism of the intestinal mucosa and the gut microbiota and their abundance changes according to the specific effects of intestinal diseases on these processes (Chan 2016).

We have demonstrated that faecal VOCs are relatively stable over time within and between individuals despite day-to-day variation in diet and are not affected by freezing and storage of stool samples ([name]; personal communication; PhD Thesis). We have optimized procedures for stool handling for metabolite extraction for gas chromatography-mass spectrometry (GC-MS) analysis (sample volume, solid phase micro-extraction fibre coating, extraction conditions [temperature and time] and vial volume; Reade 2014) and also developed the advanced statistical methods required for determining and comparing VOC profiles (Aggio 2016).

We have shown that the analysis of VOCs separates adult patients with diarrhoea-predominant irritable bowel syndrome (n=30) from those with active CD (62) and UC (n=48; sensitivity of 94% and 96% and specificity of 82% and 80% respectively; p<0.05). Our data in adults strongly suggests that VOCs differentiate CD from UC, and also Crohn's colitis from UC (Ahmed 2013). More recently, we have shown that VOCs also distinguish between active and inactive CD and UC in adult patients (Ahmed 2016).

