3.5 Secondary endpoints/outcomes

1. Faecal VOCs according to IBD diagnosis, distribution and severity at initial presentation

A diagnosis of IBD will be based on gastrointestinal endoscopy and biopsy and imaging. IBD type will be classified according to standard clinical guidelines (Levine 2014). The distribution of disease and associated manifestations (e.g. presence of fistulas) in CD will be classified according the Paris classification (Levine 2011). The severity of IBD at initial diagnosis will be graded according to paediatric-specific disease activity scores: weighted Paediatric Crohn's Disease Activity Index (wPCDAI) and Paediatric Ulcerative Colitis Activity Index (PUCAI; Ruemmele 2014).

2. Faecal VOCs in children with IBD according to response to treatment at 3 months after diagnosis

Treatment of IBD will follow established clinical guidelines. After 3 months of treatment, faecal VOCs will be compared in children who have and have not achieved clinical remission. Clinical remission in CD will be defined as a wPCDAI \leq 12.5 and in UC as PUCAI <10 points in the absence of corticosteroid treatment (Ruemmele 2014).

3. Analysis of faecal fungi in relapse of IBD

A change in the faecal mycobiome may be associated with relapse of IBD, as indicated by the presence of fungal metabolites amongst the VOCs reported in adults with Crohn's disease. If presence, this would open new avenues of treatment based on probiotics and or antifungals. VOCs may be used to monitor the effect of such therapy.

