7.7 Trial assessments

A diagnosis of IBD will be based on gastrointestinal endoscopy and biopsy and imaging and IBD type classified according to standard clinical guidelines (Crohn's disease, ulcerative colitis, indeterminate colitis; Levine 2014). The distribution of disease and associated manifestations (e.g. presence of fistulas) in CD will be classified according the Paris classification (Levine 2011). The severity of IBD at initial diagnosis will be graded according to paediatric-specific disease activity scores: weighted Paediatric Crohn's Disease Activity Index (wPCDAI) and Paediatric Ulcerative Colitis Activity Index (PUCAI; Ruemmele 2014). Treatment of IBD will be provided by clinical staff and follow established clinical guidelines.

For other conditions, specific investigations and diagnosis will be guided by clinical assessment; e.g.

Faecal volatiles in children with inflammatory bowel disease

serum anti-tissue transglutaminase antibodies and/or small bowel biopsy for the diagnosis of coeliac disease; stool bacterial culture for infectious diarrhoea. Appropriate treatment will be provided by clinical staff.

The clinical records of all children will be reviewed at 3 months after recruitment and information regarding results of investigations and diagnosis/diagnoses will be recorded.

In children with IBD, a further stool sample will be requested at 3 months. This will be used for measurement of faecal calprotectin as part of routine clinical care and, if young people or parents/guardians agree, for repeat measurement of VOCs as described above. Treatment received will be recorded and current disease activity determined. Clinical remission in CD will be defined as a wPCDAI ≤12.5 and in UC as PUCAI <10 points in the absence of corticosteroid treatment (Ruemmele 2014).

- 7.8 Long term follow-up assessments: Participants will not be followed-up after 3 months.
- 7.9 Qualitative assessments Nested studies: N/a
- 7.10 Withdrawal criteria: N/a

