10.1 Sample size calculation

Given the high sensitivity of FC in identifying children with IBD (0.98; 95% CI 0.95–1.0; Henderson 2014), we have based the sample size calculation on demonstrating that faecal VOCs have a higher specificity in identifying IBD than FC. We require 88 children with suspected IBD to demonstrate that VOCs has a better specificity of 0.80 than the specificity of 0.68 reported for FC (Henderson 2014) with 80% power at the 0.05 significance level.

Given the non-invasive nature of our study, we plan to increase the number of children recruited to also assess the ability of VOCs to differentiate between CD and UC. We plan to exceed the numbers of adults with active IBD that demonstrated excellent separation between CD and UC in our previous study (110 patients; Ahmed 2016). Our hospital IBD databases indicate that amongst new cases, two-thirds have CD and one-third UC. In our clinical experience, IBD is confirmed in 1 in 2 children with suspected IBD. To achieve sufficient power, we will recruit a total of 286 children with suspected IBD.

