10.5 Adjusted analysis - N/a

10.6 Interim analysis and criteria for the premature termination of the trial: N/a

10.7 Subject population

All participants in whom analysis of faecal VOCs is completed will be included in the study analysis.

The analysis of faecal VOCs according to response to treatment in IBD will include all children diagnosed with IBD in whom faecal VOCs are analysed 3 months after treatment.

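### The month-3 remission comparison takes all IBD children together without accounting for disease type, so a CD-versus-UC signal could pass for a remission signal if remission proportions differ between the two

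*Protocol*

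**What the plan says.** - **Population.** Protocol 10.7 says the analysis by response to treatment "will include all children diagnosed with IBD in whom faecal VOCs are analysed 3 months after treatment". It makes no split by disease type.
- **Contrast.** Protocol 3.5 says: "After 3 months of treatment, faecal VOCs will be compared in children who have and have not achieved clinical remission".
- **Outcome.** Protocol 7.7, repeating 3.5, says: "Clinical remission in CD will be defined as a wPCDAI ≤12.5 and in UC as PUCAI <10 points in the absence of corticosteroid treatment". No definition is given for indeterminate colitis, although sections 3.2 and 7.7 list it as an IBD type.
- **Method.** Section 10.3.3 applies analyses like those of the primary outcome, which is a two-group comparison. Section 10.5 marks adjusted analysis as not applicable. The subgroup section (10.4) concerns non-IBD children. The logistic models in 10.9 concern diagnosis of IBD and name age, sex and region, not disease type.
- **VOCs and disease type.** Section 1 says of the investigators' adult data that they "strongly suggests that VOCs differentiate CD from UC". Section 10.1 says that adults with active IBD "demonstrated excellent separation between CD and UC in our previous study (110 patients". Section 3.2 makes the same separation an objective in children.

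**The concern.** Disease type could confound the month-3 comparison if two links hold.

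1. **Type to VOCs.** This is the protocol's own working premise, from adult data.
2. **Type to outcome.** Remission is judged on one index and cut-off in CD and on another in UC. Equal remission proportions therefore cannot be presumed, though unequal ones are not shown either.

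If both hold, a marker or classifier that recognises CD is associated with the remission label even if it carries no information on disease activity. The cross-validation and Monte Carlo randomisation in section 7.11 do not remove this, because type would also predict the label in held-out children. Control of the false discovery rate does not remove it either.

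The comparison answers the second of the three main research questions in section 3, and it supports the stated hope that VOCs can monitor IBD. By month 3 the child's disease type is normally known, so the useful question is whether VOCs separate remission from persistent disease within a type. An unstratified result does not isolate that.

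**Working it through.** **The plan's own figures.** The protocol gives no sample size, remission rate or expected AUROC for the month-3 comparison. Its only powered figure, 88 children for specificity 0.80 against 0.68, reproduces as (1.960 + 0.842)² × 0.80 × 0.20 / 0.12² = 87.2, rounded up to 88. It does not bear on this point.

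**Inputs from the protocol.** 143 IBD cases (10.2), two-thirds CD and one-third UC (10.1): 143 × 2/3 ≈ 95 CD and 143 / 3 ≈ 48 UC.

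**Assumed inputs.** Remission proportions in CD and UC, the distance *d* (in SD) between CD and UC on a VOC marker, and the return of month-3 samples. The protocol gives none of these.

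**Step 1. What disease type alone can achieve.** Let r be the proportion in remission in each disease.

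- P(CD | remission) = n_CD r_CD / (n_CD r_CD + n_UC r_UC)
- P(CD | persistent) is the same with 1 − r in place of r
- AUROC of type alone = 0.5 + 0.5 × |difference between the two|
- Expected gap between the outcome groups, for a marker that differs only by type = *d* × that difference

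Example with 95 CD and 48 UC, remission 75% and 45%:

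- P(CD | remission) = 71.25 / (71.25 + 21.6) = 0.767
- P(CD | persistent) = 23.75 / (23.75 + 26.4) = 0.474
- AUROC = 0.5 + 0.5 × 0.294 = 0.647
- At *d* = 1.5 the false group gap is 1.5 × 0.294 = 0.44 SD

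**Step 2. False-positive rate with imperfect separation.** This simulation used 4,000 runs per setting with 95 CD and 48 UC. The marker is unrelated to remission within each disease. The test is a two-sided t-test at 0.05 of remission against no remission.

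| Remission CD / UC (assumed) | AUROC, type alone | *d* = 0.5 | *d* = 1.0 | *d* = 1.5 |
|---|---|---|---|---|
| 60% / 60% | 0.50 | 5.6% | 5.1% | 5.0% |
| 65% / 55% | 0.55 | 6.2% | 8.0% | 10.6% |
| 70% / 50% | 0.60 | 8.9% | 15.8% | 26.6% |
| 75% / 45% | 0.65 | 12.6% | 33.8% | 53.9% |
| 50% / 70% | 0.59 | 8.0% | 16.2% | 26.6% |

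The last row shows that the direction of the gap does not matter. The same test with disease type as a covariate stays between 4.5% and 5.6% throughout. That is within simulation error of 5% (standard error √(0.05 × 0.95 / 4000) = 0.34 points).

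**Step 3. Upper bound: perfect recognition of type.** Assume 80% of cases return a sample: 143 × 0.8 ≈ 114, that is 76 CD and 38 UC. If VOCs identify type perfectly and carry no activity information, the test reduces to a 2×2 table of type by remission (chi-square, no continuity correction). The last column gives the single-marker test of Step 2 for the same numbers of children.

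| Remission CD / UC (assumed) | AUROC | p<0.05, perfect recognition | p<0.05, *d* = 0.5 / 1.0 / 1.5 |
|---|---|---|---|
| 70% / 60% | 0.55 | 19% | about 5% / 8% / 10% |
| 75% / 50% | 0.63 | 76% | about 9% / 21% / 35% |
| 80% / 50% | 0.66 | 91% | about 12% / 29% / 50% |

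For the first row, P(CD | remission) = 53.2 / 76.0 = 0.70 and P(CD | persistent) = 22.8 / 38.0 = 0.60, so AUROC = 0.5 + 0.5 × 0.10 = 0.55.

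**The case against.** **The quoted sentence fixes a population, not a model.** Section 10.7 says whose samples enter, the word 'pooled' appears nowhere, and a separate SAP is promised. Section 7.11 also has GCMS reports built by group, with CD and UC apart. This has some force: stratification is the kind of detail a SAP may supply. But the protocol does more than stay silent. It describes a single two-group contrast and marks adjusted analysis as not applicable, and the grouped GCMS reports are not tied to month 3. Section 10.8 mentions a covariate-adjusted analysis, which sits awkwardly with 10.5, but it names no disease-type covariate.

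**Unequal remission rates are not shown.** This stands. A reader might infer from the two indices and cut-offs that remission rates will very likely differ between CD and UC. The documents do not support that. They give no rates, and two disease-specific cut-offs do not by themselves imply different proportions. With equal rates there is no bias.

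**Strong separation by type is not shown in this setting.** This also stands. The evidence comes from adults with active disease. The Background warns that adult performance cannot be assumed in children, and that colonic inflammation in children makes CD and UC harder to tell apart. Perfect recognition is therefore a bound, not an expectation.

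**A type-only classifier would not look impressive.** A reader might infer that it could score well. Even with perfect recognition and a 30-point gap, the AUROC is only 0.66. What it can do is exceed chance, and that could be read as an activity signal.

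**The endpoint is secondary, unpowered and exploratory, and the stated objective concerns children with IBD as a whole.** That is fair. It argues for keeping the all-IBD result in view and against treating the point as critical. It does not remove the ambiguity in what that result would mean.

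**Conclusion.** The concern holds in conditional form. As written, the plan leaves disease type as a possible confounder of the month-3 remission comparison. Whether it biases the result depends on remission proportions that the protocol does not give.

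- Equal proportions: about 5% false positives, so no harm.
- Gaps of 10 to 30 points with type separation of 0.5 to 1.5 SD (95 CD, 48 UC): about 6% to 54%.
- Perfect recognition of type (76 CD, 38 UC), an upper bound: AUROC 0.55 to 0.66, with p<0.05 in about 19% to 91%.

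The documents do not support saying that the month-3 result will be spurious, or that a type-only classifier would perform well. They do support saying that an above-chance all-IBD result could not, by itself, be read as evidence about disease activity. The correction is cheap and should be made. Separately, children with indeterminate colitis fall within the all-IBD population but have no stated remission definition.

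**What to change.** In sections 10.3.3, 10.5 and 10.7:

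1. State that the month-3 comparison accounts for disease type, by a stratum or a covariate. Where labels are permuted, permute within type.
2. Report performance within CD and within UC beside the all-IBD result.
3. Base any claim that VOCs distinguish remission from persistent disease on the type-adjusted result.
4. Replace the not-applicable entry in 10.5 accordingly, and reconcile it with the reference to covariate adjustment in 10.8.
5. State how children with indeterminate colitis enter this analysis, since no remission definition is given for them. That definition is a clinical matter for the investigators.

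**Cost.** Wording changes and a few extra runs on data already being collected. The UC results will be imprecise: about 38 children if 80% return a sample, so a wide interval and limited scope for a separately cross-validated classifier. A type-adjusted analysis across both diseases still uses all the CD and UC data.

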10.8 Procedure(s) to account for missing or spurious data

Maximum efforts will be made to avoid missing values in the database. However, where this does occur, missing covariates will be imputed using simple imputation methods in the covariate adjusted analysis based on the covariate distributions. For a continuous variable, missing values will be imputed from random values from a normal distribution with mean and SD calculated from the sample. For a categorical variable, missing values will be imputed from random values from a uniform distribution with probabilities P1, P2, ..., and Pk from the sample. For count data, missing values will be imputed from random values from a Poisson distribution with λ from the sample. Seed for the imputation is set as 128.

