7.5 Unblinding: N/a

7.6 Baseline data

Demographic, environmental and clinical information will be collected onto standard forms:

- Demographic information will include age, gender, ethnicity
- Clinical information will include anthropometry, main presenting gastrointestinal symptoms and signs, current diet (e.g. vegan), current medication, treatment with oral/parenteral antibiotics or anti-fungal agents in the last 3 months
- Environmental factors will include: number of siblings at home, smoker in the household, household pets, urban/rural residence, foreign travel in last 3 months

The results of routine clinical baseline investigations if done will be recorded:

- In blood: haemoglobin, white cell count, inflammatory markers (platelets, C-reactive protein, ESR), albumin, liver function tests, urea, creatinine, test for coeliac disease
- In stool: calprotectin, C. difficile toxin, bacterial culture
- Imaging: X rays and scans

Further investigations will be planned according to the initial clinical assessment in accordance with usual clinical practice.

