10.9 Other statistical considerations

In addition to the main analyses described above, we also plan to undertake extensive statistical analysis to explore whether combining VOC data with faecal calprotectin and possibly other inflammatory markers (e.g. CRP) increases sensitivity and specificity in the diagnosis of IBD. Multivariate logistic regression models will be used to determine the specificities and 95% confidence intervals of combinations of diagnostic tests and also explore the effects of demographic factors such as age, sex and region. Other statistical methods will be used if deemed necessary.

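### Section 10.8 fixes single, unconditional random-draw imputation; if applied to calprotectin or CRP in the exploratory 10.9 models, it dilutes those markers and inflates the apparent gain of VOC+FC over FC alone

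*Protocol*

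**What the plan says.** Section 10.8 sets the method out in full. Its general rule is that "missing covariates will be imputed using simple imputation methods in the covariate adjusted analysis based on the covariate distributions". Variables measured on a continuous scale come under this line: "missing values will be imputed from random values from a normal distribution with mean and SD calculated from the sample". Categories are handled in a parallel way, in that "missing values will be imputed from random values from a uniform distribution with probabilities P1, P2, ..., and Pk from the sample"; counts are drawn from a Poisson distribution. The section ends by fixing the seed: "Seed for the imputation is set as 128". Multiple imputation and pooling of variances are not mentioned.

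Three other places bear on what the rule can affect:

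- **Adjusted analysis.** The heading reads "10.5 Adjusted analysis - N/a".
- **Section 10.9.** Logistic models will "explore whether combining VOC data with faecal calprotectin and possibly other inflammatory markers (e.g. CRP) increases sensitivity and specificity in the diagnosis of IBD". They are to give specificities with 95% confidence intervals for combinations of tests, and to explore age, sex and region.
- **Sections 7.6 and 10.7.** "The results of routine clinical baseline investigations if done will be recorded", and this list includes calprotectin and CRP. The analysis set is every participant with a completed VOC analysis.

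**The concern.** A value drawn from the pooled distribution carries no information about whether the child has IBD. Putting such values into a diagnostic model adds noise to the imputed marker and to nothing else. VOCs are complete by definition of the analysis set, so any noise falls on the conventional markers. If those markers are imputed under 10.8, the comparison of VOC+FC with FC alone is tilted towards VOCs.

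Two lesser defects follow from the same rule. Single draws treated as observations ignore imputation uncertainty, so the planned 95% intervals are too narrow. Normal draws for a right-skewed marker on its raw scale can be negative.

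The Background argues that the low specificity of FC calls for an alternative or additional test. Section 10.9 is the only planned analysis of the additional role, so a built-in tilt there matters even though the analysis is exploratory.

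**Working it through.** Section 10.8 states no figure, so there is none to reproduce. The check calibrates FC to the protocol's own accuracy and applies the rule.

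**Inputs from the protocol.** FC sensitivity 0.98 and specificity 0.68, 286 children, IBD confirmed in 1 in 2 (section 10.1).

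**Assumptions.** FC is normal with equal SD in both groups on a suitable scale. VOC has sensitivity and specificity of 0.80; the protocol gives only the 0.80 specificity, as its target. Within-group FC-VOC correlation is 0 or 0.5. The missing fraction m is 5 to 20% and equal across groups.

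**1. Calibration.** The separation of the FC means is z(0.98) + z(0.68) = 2.054 + 0.468 = 2.521 SD. The FC AUC is Φ(2.521/√2) = 0.963. The pooled SD is √(1 + 2.521²/4) = 1.609.

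**2. Fixed cut-off.** The cut-off is 0.468 and the pooled mean is 2.521/2 = 1.261. A draw is positive with probability Φ((1.261 − 0.468)/1.609) = 0.689, whatever the diagnosis. So:

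- sensitivity = (1 − m) × 0.98 + m × 0.689
- specificity = (1 − m) × 0.68 + m × 0.311

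| m | sensitivity | specificity |
|---|---|---|
| 0 | 0.980 | 0.680 |
| 5% | 0.965 | 0.662 |
| 10% | 0.951 | 0.643 |
| 20% | 0.922 | 0.606 |

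The difference in mean FC between the groups shrinks by the factor (1 − m).

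**3. FC AUC in closed form.** A measured IBD value exceeds a draw with probability Φ(1.261/√(1 + 1.609²)) = 0.747, and by symmetry a draw exceeds a measured non-IBD value equally often. So AUC = (1 − m)² × 0.963 + 2m(1 − m) × 0.747 + m² × 0.5. At m = 10% this is 0.780 + 0.134 + 0.005 = 0.919. At m = 20% it is 0.616 + 0.239 + 0.020 = 0.875.

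**4. Combined model by simulation.** n = 286, half with IBD, logistic model of diagnosis on FC and VOC, 200 to 400 runs per row. Columns are summarised separately, so the gain can differ by 0.001 to 0.003 from the difference of the two AUCs.

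| Correlation | m | FC AUC | VOC+FC AUC | gain over FC |
|---|---|---|---|---|
| 0 | 0 | 0.964 | 0.985 | 0.021 |
| 0 | 5% | 0.939 | 0.974 | 0.033 |
| 0 | 10% | 0.920 | 0.965 | 0.044 |
| 0 | 20% | 0.877 | 0.948 | 0.070 |
| 0.5 | 0 | 0.963 | 0.966 | 0.003 |
| 0.5 | 5% | 0.940 | 0.952 | 0.010 |
| 0.5 | 10% | 0.918 | 0.940 | 0.019 |
| 0.5 | 20% | 0.878 | 0.927 | 0.048 |

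A repeat at 10% gave gains of 0.046 and 0.021. The simulated FC AUCs agree with step 3.

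**5. The other contrast.** VOC alone has separation 2 × z(0.80) = 1.683 and AUC Φ(1.683/√2) = 0.883. The gain of the combination over VOC alone falls from 0.985 − 0.883 = 0.102 to 0.948 − 0.883 = 0.065 at 20% missing (correlation 0), and from 0.966 − 0.883 = 0.083 to 0.927 − 0.883 = 0.044 (correlation 0.5).

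**6. Is the rule the cause, or the missing data?** At 20% missing, complete cases gave an FC AUC of 0.963 and gains of 0.022 and 0.003. One draw conditional on diagnosis and VOC gave 0.963, with gains of 0.021 and 0.003. Both recover the full-data result, so the rule is the cause. The direction was the same when missingness was three times as frequent in non-IBD children.

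**7. Negative draws.** For a normal draw with coefficient of variation CV, P(draw < 0) = Φ(−1/CV): 16% at CV 1 and 25% at CV 1.5. Both CVs are assumed.

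**The case against.** The strongest reply is that FC and CRP may never be imputed. Section 10.8 speaks only of covariates and names neither marker. Section 10.9 distinguishes combinations of diagnostic tests from demographic factors. The Poisson rule suits the number of siblings in section 7.6 better than any inflammatory marker. This stands: applying the rule to FC and CRP is an inference. But 10.8 does not exclude them, they are predictors in the only models the rule can reach, and they are recorded only where performed.

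The missing fraction for FC may also be small. Section 7.1.2 has the stool tested for calprotectin as routine, the VOC aliquot comes from the routine stool sample (section 7.11), and incomplete data are followed up by telephone (section 11.1). This too stands. The upper rows of the table may not be reached for FC. CRP and the other blood tests carry no comparable assurance, though only FC was modelled.

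A reader might infer three stronger things that the documents do not support:

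- **That the rule destroys the association between marker and diagnosis.** It is lost only among the imputed values; overall it is diluted by the missing fraction.
- **That the study will exaggerate the value of VOCs in general.** The inflation concerns VOC+FC against FC alone, a contrast the protocol does not fix. The combination's own accuracy and its gain over VOC alone are understated.
- **That the main result is at risk.** The primary GCMS and Odoreader comparisons use no imputed covariates, and 10.9 is additional and exploratory.

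Finally, the detail of a replacement method could be left to the SAP. That does not excuse a protocol that already fixes an unsuitable one.

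**Conclusion.** The point holds within limits. The rule is wrong as written: it attenuates any covariate to which it is applied, and it makes the promised intervals too narrow (the narrowing was not quantified). Its stated setting, a covariate-adjusted analysis, conflicts with section 10.5.

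If FC falls under the rule, even 5 to 10% missing roughly doubles the apparent AUC gain over FC when VOC and FC are independent. At correlation 0.5, where VOC adds almost nothing, 10% missing turns a gain of 0.003 into about 0.02. These sizes rest on the binormal model, the assumed 80/80 VOC accuracy and the assumed missing fractions; the direction does not depend on the exact values tried. The consequence is confined to the exploratory combined-test models. Severity: should-fix.

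**What to change.** - Delete the marginal-draw rules and the seed from section 10.8.
- Fit the 10.9 combined-test models in children with the relevant markers measured, and report the number missing for each marker by final diagnosis.
- As a sensitivity analysis, use multiple imputation with Rubin's rules, conditional on diagnosis, VOC score and the other covariates, with skewed markers transformed first. This is needed because tests done on clinical grounds may not be missing completely at random.
- Reconcile sections 10.5, 10.8 and 10.9: state which models are adjusted, and which variables count as covariates and which as tests under evaluation.

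The cost is a change of wording, standard software and slightly fewer children in the combined-test models. The change should be made before the data are analysed.
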